#### Secondary Analyses

To examine the effects of treatment with each secondary EMA endpoint including fatigue/sleepiness, positive affect, and negative affect, we will employ the model described above (i.e., same approach as used in the primary analysis). To examine the effects of treatment on 1) sleep continuity variables (sleep onset latency, wake after sleep onset, sleep efficiency, and total sleep time) as measured by sleep diary and actigraphy, 2) self-report questionnaires, and 3) cognitive testing, scores will be compared both within and between-groups adjusting for baseline values using analysis of covariance (ANCOVA). This procedure is known to maximize power.

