### Design

This is a single-site, double-blind, randomized, placebo-controlled clinical trial. The study employs a two-group (suvorexant, 20mg, qhs, versus placebo) parallel design and involves remote (baseline) assessments, 16-day active treatment phase with intensive ambulatory monitoring via wrist actigraphy and ecological momentary assessment (EMA). Outcome

assessments are conducted at two weeks while participants are on study treatment or placebo and include self- report questionnaires and comprehensive cognitive testing administered by computer.

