#### **Eligibility/Consenting/Phone Call**

Participants will receive the study consent form via email (or via snail mail if requested). The study team will work with potential participants to complete the informed consent process. Participants will provide their signed consent to participate in the study. Once signed consent is confirmed, participants will complete the remote assessments. Then the study staff will confirm eligibility and the sleep expert (i.e., PI) will confirm individual's study participation.

Once study participation is confirmed, the participant will be randomized to drug or placebo in a 1:1 ratio by the IDS pharmacy. Throughout the study participants will wear an actigraph. An actigraph is a wristwatch-like device that detects ambulatory movement, a validated proxy for sleep. Participants will also complete brief surveys four times per day for 16 days. At post-treatment, participants will complete validated questionnaires, neurocognitive tasks, and a brief satisfaction survey. Additional details presented below.

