### **Remote Assessments (Day 0)**

Study staff will schedule a time for participants to complete the remote assessments. These include a semi-structured interview, validated questionnaires (about 45-60 minutes), and computerized neurocognitive tasks (about 15-20 minutes). Participants will complete the remote assessments over one day (90 minutes) or two days (about 45 minutes each day). For participants who prefer to complete the remote assessments over two days, the first day will include the consent and interview. The second day will include the validated questionnaires and neurocognitive tasks.

Participants use a special research smartphone app for this study, which will capture daily surveys (described below). All study tasks will be remote, e.g., over the phone or via secure teleconferencing platforms like Zoom. During the remote assessments, participants will have many breaks to help them stay refreshed. Participants can also request a break after any task.

Neurocognitive tasks are computerized measures that include the psychomotor vigilance test (PVT), Stroop Task, and a Task-switching exercise developed for use among older adults. To help participants complete these tasks, study staff will email or text participants a link, which will enable completion of the computerized tasks on participants' smartphone, laptop, or desktop computer. In the tasks participants will be asked to respond to words, shapes, and colors on their screens.

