### **Actigraphy Setup (Days 1-16)**

Once participants complete the remote assessments participants will set up their actigraph with study staff. Study staff will contact participants to review instructions and inquire of general questions of quiet time activities remotely e.g., over the phone or via secure teleconferencing platforms like Zoom. Participants will be instructed to wear an actigraph on their non-dominant hands for approximately 16 days. We will mail participants an actigraph along with a pre-paid mailing envelope. Actigraphs are expensive

research devices and must be returned. Study staff will call to remind participants when it is time to return the actigraph.

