### **Daily Survey Completion (Days 1-16)**

While participants wear the actigraph, they will also complete brief surveys on their mobile phones. The surveys are sent to participants 4 times a day for 16 days. Each survey takes less than 2 minutes to complete. Participants' phones will send them notifications for each survey. At the start of the study, participants will choose what time they want surveys to start. Every morning, participants will complete a survey that includes a brief sleep diary and questions about generalized quiet time activities and how they feel. Next, participants will complete three more surveys throughout the day. These surveys also ask about how they feel. These surveys will be given at random times throughout the day, about two hours apart over the next 12 hours. Study staff will be available to answer any questions or give support. Contact information for study staff and technical support will be given to them.

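### The ANCOVA for the sleep outcomes adjusts for a baseline that actigraphy never has and that the diary has, at most, in one undesignated entry

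*Combined protocol and SAP*

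**What the plan says.** Secondary Analyses puts three outcome groups under one sentence: the sleep continuity variables by diary and actigraphy (total sleep time, sleep efficiency, sleep onset latency, wake after sleep onset), the self-report questionnaires, and the cognitive tests. For all of them, "scores will be compared both within and between-groups adjusting for baseline values using analysis of covariance (ANCOVA". The reason given is "This procedure is known to maximize power".

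The Design section describes the study as "remote (baseline) assessments, 16-day active treatment phase with intensive ambulatory monitoring via wrist actigraphy and ecological momentary assessment (EMA", so the remote assessments are the only component labelled baseline. Their content is listed under Remote Assessments (Day 0): "These include a semi-structured interview, validated questionnaires (about 45-60 minutes), and computerized neurocognitive tasks (about 15-20 minutes". A home sleep apnea test, which evaluates breathing, is also placed on Day 0.

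The two sleep instruments come later. Under Actigraphy Setup (Days 1-16), "Once participants complete the remote assessments participants will set up their actigraph with study staff", and "Participants will be instructed to wear an actigraph on their non-dominant hands for approximately 16 days". Under Daily Survey Completion (Days 1-16), "Every morning, participants will complete a survey that includes a brief sleep diary". The treatment section gives a two-day initial step and then a 14-day period, 16 pill nights in all. No section ties the first pill to a numbered study day.

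**The concern.** A baseline-adjusted ANCOVA needs a pre-treatment value of the outcome, and a within-group comparison needs one as its reference. For actigraphy the schedule provides neither. For the diary a value may exist, but no entry is named as baseline and the documents do not show whether the first entry is pre-dose.

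The analyst would have to drop the adjustment, pick a baseline night once data are in hand, or use a night after the first pill. The last choice does the most harm: it conditions on a value that treatment may already have changed, and so can remove part of the effect being estimated. The second leaves a discretionary choice in an analysis that should be fixed in advance. In either case the power argument for ANCOVA does not carry over to these outcomes unless a valid baseline exists.

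**Working it through.** **1. Where each ANCOVA outcome gets its baseline**

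| Outcome group | Scheduled before the first pill? | Section |
|---|---|---|
| Questionnaires | Yes, Day 0 | Remote Assessments (Day 0) |
| Cognitive tests | Yes, Day 0 | Remote Assessments (Day 0) |
| Actigraphy, 4 variables | No | Actigraphy Setup (Days 1-16) |
| Diary, 4 variables | Not stated; at most the Day 1 morning entry | Daily Survey Completion (Days 1-16) |

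The sleep analyses number 4 variables x 2 instruments = 8, with two different gaps of 4 each.

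**2. Counting nights**

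Pill nights: 2 + 14 = 16. Monitoring: Days 1-16, which is 16 days inside the treatment phase. Two placements of the first pill are compatible with the text:

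- Bedtime on Day 1: 0 pre-pill actigraphy nights within Days 1-16, and 1 of 16 diary entries (the Day 1 morning entry describes the night before).
- The night before Day 1: 0 pre-pill actigraphy nights and 0 diary entries.

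The actigraphy result is the same under both. The diary result depends on which holds.

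**3. What a post-pill baseline would do**

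Let d be the true effect, r the correlation between the stand-in night and the outcome (equal SDs), and f the share of the effect already present on that night. ANCOVA then estimates d(1 - r x f). The documents give neither r nor f, so both are assumptions. The d = 0.5 is borrowed from Sample Size, where it refers to the DISS, and serves only as a scale.

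| f | r = 0.5 | r = 0.7 |
|---|---|---|
| 0.25 | 0.438 | 0.412 |
| 0.5 | 0.375 | 0.325 |
| 1 | 0.250 | 0.150 |

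For example, 0.5 x (1 - 0.5 x 0.5) = 0.375.

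**4. Precision cost of replacement covariates**

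Sample Size gives 20 completers per arm, so N = 40. With k covariates unrelated to the outcome, the variance of the treatment contrast is proportional to 1 + k/(N - k - 3) = 37/(37 - k).

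- 0 to 3 covariates: 37/34 = 1.088; SE x 1.043 (+4.3%).
- 1 to 3 covariates: 36/34 = 1.059; SE x 1.029 (+2.9%).
- 2 to 3 covariates (age and sex already included): 35/34 = 1.029; SE x 1.015 (+1.5%).

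The last figure applies only if the ANCOVA already contains age and sex. Secondary Analyses does not say so; Main Analysis lists them for the mixed models. Against an unadjusted contrast, three covariates pay for themselves once together they explain more than 1 - 34/37 = 8.1% of the outcome variance.

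**5. Precision given up without a baseline**

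A true baseline with correlation r multiplies the SE by about sqrt(1 - r^2): 0.87 at r = 0.5 and 0.71 at r = 0.7 (r assumed).

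**6. Missing Day 1 diary entries**

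Main Analysis expects more than 80% completion. If Day 1 mornings are missed at the same rate as other surveys, at most 0.2 x 20 = 4 per arm would lack the entry.

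**The case against.** Three points can fairly be made for the plan.

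First, an untreated actigraphy night may occur in practice. Set-up follows the remote assessments, wear is only approximately 16 days, and Eligibility/Consenting/Phone Call says that the device is worn throughout the study. This stands as a possibility for some participants, but none of these statements schedules such a night or names it as baseline.

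Second, with a bedtime pill, 16 pill nights and days numbered 1-16, it is natural to match each pill to that day's bedtime. The Day 1 diary entry would then be pre-dose, and the diary would need only one designating sentence. That reading is plausible, but the documents do not state it.

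Third, the harm is limited. These are secondary outcomes in a preliminary study, and randomization protects the between-group contrast with or without a baseline term. This stands in full. Use of a post-pill night is a risk that the wording leaves open; the plan does not say that it will be done.

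A reader might also infer that the primary EMA analysis is compromised, because its model has no baseline term and Day 1 surveys may precede the first pill. The documents do not support that. Main Analysis defines the endpoint across the study period, with covariates limited to age and sex, and that contrast is valid under randomization.

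**Conclusion.** The point holds for the diary and actigraphy outcomes in Secondary Analyses, and should be fixed before the data are analysed. For the 4 actigraphy analyses, neither the stated covariate nor the within-group reference exists in the schedule, wherever the first pill falls among the readings that the text allows. For the 4 diary analyses, at most 1 of 16 entries could serve, and its status depends on a first-pill day that is not stated.

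It would go too far to conclude that all 8 analyses are equally impossible, or that the sleep comparisons are biased as planned. The diary may need only a designation, and a between-group contrast without a baseline term is unbiased. Questionnaires and cognitive tests are not affected, since they are measured on Day 0 and again at post-assessment.

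The schedule finding needs no numerical assumption. The attenuation figures are illustrations resting on assumed r and f. No power figure is claimed for the sleep outcomes, because the documents give no baseline correlation.

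**What to change.** - Reconcile Actigraphy Setup, Daily Survey Completion and the treatment section so that the first-pill day relative to Day 1 is stated.
- State in Secondary Analyses that no night after the first pill may serve as baseline.
- Actigraphy: drop the baseline term and the within-group change. Compare groups adjusting for age and sex, as in Main Analysis. Add one prespecified Day 0 sleep questionnaire score only if a suitable one is collected; Remote Assessments (Day 0) names no instrument.
- Diary: if the Day 1 morning entry is pre-dose, name it as baseline and put missing values into the planned multiple imputation. If it is not pre-dose, analyse the diary as for actigraphy.
- Base treatment conclusions on the between-group contrasts.

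The cost is wording only, with no new visit, device time or participants. The statistical price is the small SE increase in step 4 if the covariates prove uninformative. For any outcome that loses its baseline term, the power gain that the plan claims for ANCOVA is also given up.

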### **Post Assessment**

Post Assessment Satisfaction Survey: A brief user experience/satisfaction survey will be administered to participants following the completion of the 16-day continuous monitoring phase.

### **Safety Monitoring**

If a potential participant indicates thoughts of self harm, they will administratively withdrawn from the study. These individuals will be referred to the Carruthers Clinic/Outpatient Mental Health at the UMMC-Midtown Campus, as well as advised to contact their primary care providers (or mental health professional if they have one), to call or text the national suicide hotline directly at 988 (or [contact]), 911, and/or to report

to their nearest emergency room. For all withdrawals due to thoughts of self-harm, the PI will follow-up to ensure this was done, or that adequate alternative steps were taken. Participants who are withdrawn from the study will be compensated for study procedures completed.

## **NEUROCOGNITIVE TESTING**

### **Assessments**

General neurocognitive function will be assessed by using computerized testing which can be completed via a software package developed specifically for remote administration. Measures to be administered include sustained attention (psychomotor vigilance task [PVT]), inhibition (Stroop task), and task-switching/executive function (task-switching task). Participants will receive a link to complete the neurocognitive tasks. These tasks can be completed in approximately 15-20 minutes via smartphone, laptop, or desktop computer. It should be noted that no PHI will be entered or transmitted, participants will be identified using only a participant ID.

To complete the three computerized tasks (Stroop, PVT, Task-Switch), participants will be emailed the link to download each task. Study staff will instruct participants on how to download the link and open the tasks on their home computer. Once the task is open, it will prompt participants to enter their unique ID. Study staff will stay on the phone with participants for the duration of the computerized tasks to provide technical support if needed. After participants complete each computerized task, their data will be automatically sent to the researchers. Participants will have breaks in between each individual task and based on participant need.

## **RECRUITMENT**

### **Inclusion/Exclusion Criteria**

#### *Inclusion*

1. Age 60-85 years old.
2. Meets Diagnostic and Statistical Manual – Fifth Edition (DSM-5) diagnostic criteria for chronic insomnia disorder.

#### *Exclusion*

1. High risk for untreated organic sleep disorders other than insomnia (narcolepsy, periodic limb movement disorder, etc) as determined by structured clinical interview and investigator clinical judgment.
2. Current diagnosis of an untreated major medical (e.g., diabetes, heart disease) or psychiatric (e.g., bipolar disorder) disorders.
3. History of suicide attempt within past 5 years.
4. History of alcohol or substance abuse (including prescription medication abuse) within past 5 years.
5. Heavy alcohol consumption (e.g., >5 drinks per day or > 14 drinks per week).
6. Heavy caffeine use (>4 cups of coffee/day [equivalent]).
7. Current tobacco or nicotine use.

8. History of previous allergic reaction, sensitivity, or severe side effects to sedative hypnotics.
9. Moderate/strong CYP3A inhibitors.
10. Refusal to discontinue or intent to initiate non-study prescription, OTC, or other sleep aids during study period.
